The typical range from highest threshold luminance to absolute rod threshold covers about 5 logarithm units of luminance [16]. The first part of the curve is the photopic phase, which identifies the cone adaptation. The last part of the curve is the scotopic phase, which identifies the rod adaptation [11]. The interval between the two phases is commonly referred to as the rod-cone break. It can be seen in Figure 1 that, as the luminance is reduced, there is an increase in light sensitivity, which is initially very rapid before levelling off after 5 to 10 minutes at the final or absolute cone threshold [5]. At this point, the foveal cone cells are fully dark adapted (i.e., they have reached their maximum sensitivity [17]); in contrast, the rod cells are saturated and inactive [1]. With time (the luminance of the stimulus is reduced) a second slower fall in the threshold luminance is observed as the peripheral rod cells become activated (rhodopsin is regenerated). Rod adaptation is slower than the cone adaptation [18] because of the regeneration half-life of the visual pigments. However, unlike cone cells, light of very low intensity is capable of stimulating the rod cells, when given sufficient time to accumulate rhodopsin [2]. After approximately 30-40 minutes in total darkness, the final rod threshold is achieved. Dark adaptation is now complete and no further increase in sensitivity of the rods photoreceptors is possible.

The time required to reach maximum sensitivity is dependent on the amount of pigment bleached by the previous light exposure [19] and neural adaptation. The wavelength of the incident light has also a strong influence on the dark-adaptation curve, given that cone mediated vision is responsible for colour vision whereas rod vision is colourless.

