Most dark adaptometers are based on the Hecht-Schlaer adaptometer developed in the 1938 [19], which is considered the first reliable instrument allowing for an accurate investigation of the various aspects of dark adaptation after previous attempts carried out by use of photometer devices [8, 15, 24]. Variation of the light stimulus was obtained by Hecht and Schlaer upon the insertion of several neutral density filters in front of a tungsten light source. The test field subtended 3° and was presented 7° nasally to the fixation light. The fixation intensity was adjustable and was maintained so as to be just visible by the subject throughout the test. Dark adaptation data obtained from this device under controlled conditions were accurate, reliable and reproducible. Many subsequent instruments are essentially modifications and improvements on this device [25-28]. A notable device was constructed by Wald [29] in 1941 and used to survey vitamin A deficiency in Newfoundland, but with limited success. A novel landmark, low cost instrument was developed by Henson and Allen [30] in 1977 consisting of a single stimulus of a green (565 nm) solid-state light-emitting diodes (LEDs) as opposed to tungsten filaments used in earlier devices. The stimulus intensity control setting was via a manual position switch that corresponded to 12 discrete luminance light levels that were approximately half (or a quarter) the previous presentation luminance. The fixation distance was 33 cm. Electronic circuitry controlled the LED light output to a quoted accuracy of 0.1%, which could be maintained over ten years of continuous use. A potential deficiency with this

instrument was that the test was self-administered/controlled leading to possible significant bias in the test results. In addition, it lacked a chin rest, thus the distance between the stimulus and the subject appears not to have been fixed; consequently, there is an uncertainty in the exact stimulus size and eccentricity to the fovea.

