In order to overcome the associated problems with current instrumentation described above, the use of a novel, wearable and semi-automated dark-adaptometer is proposed. This is implemented as a pair of head-mounted googles and a handheld joystick, and it is easy to use without the need of any skilled operator. The novel dark-adaptometer is very versatile, uses low-cost solid-state electronics, and features low-power consumption, which allows for battery-powered operation. For a more comfortable user experience, the system is light and characterised by durable enclosures that totally black-out the inside of the goggles, hence avoid the need of a dark room to carry out dark-adaptometry testing.

The portability, ease of use, and relatively low cost of this system aims to spread the practice of dark-adaptometry testing and let it be adopted also by high-street optometrists. This will allow diagnosing a number of retinal pathologies more quickly and more reliably eventually bypassing the use of other visual electrophysiology equipment such as the ERG system: a more expensive instrument characterised by a larger form factor and a range of features that may be surplus to optometrists' requirements. Receiving a quick diagnosis may lead to starting a treatment sooner; faced with an ageing population, this represents a major asset to the Health Community and the NHS.

The wearable light-emitting system as described can represent a viable diagnostic tool for measuring dark-adaptation thresholds with proven good reproducibility and precision of the test data when compared to conventional instrumentation. Since the intensity, duration, colour, area and location of the light used for the fixation, bleach, and target stimuli all have an influence on the measured thresholds [8, 19, 44], the modified 3-down-1-up staircase procedure carried out in [43] will be adopted here for comparison purposes with data results reported in the literature.

3. Aim

The aim of this study is to assess dark-adaptometry testing performance of a novel wearable light-emitting system by generating full dark adaptation threshold functions in normal adult healthy volunteers.

The study intends to answer the following research questions:

- I. Is it possible to reproduce state-of-the-art threshold measurements as good or better than those produced by commercially-available dark-adaptometers and reported in the literature?

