4.3. Investigational system

[figure not shown]

Figure 3. 3-D model of the head-mounted goggles with parts

The novel dark-adaptometer is designed as a wearable and semi-automated system consisting of a pair of head-mounted goggles (Figure 3) and a handheld joystick. Within each side of the goggles are included: an organic light emitting diode (OLED) display, which delivers the light stimuli; and a LCD filter sitting in front of the display to precisely tune the light stimuli within a range between 10^{-6} to 10 cd/m^2 . A handheld joystick completes the system allowing the subject under test to wireless transmit its response to the visible light stimuli through the press of a button. The response is cached and interpreted by the computing unit inside the goggles, which automatically set light intensity and time interval of the successive stimuli based on a modified 3-down-1-up staircase procedure described as in [43] and schematically depicted in Figure 4.

[figure not shown]

Figure 4. Flow-chart of the implemented dark-adaptometry testing procedure

Wearable goggles and joystick are given to participants in their switched-on status and held by the subject under test respectively on the forehead, with an elastic strap, and on the dominant hand. In order to reset the photoreceptors of the retina, thus guarantee a similar non-dark-adapted background common to all participants, a photo-bleaching flash is presented through an external camera and channelled to the study eye at the start of the test. Immediately after the onset of the photo-bleaching flash, the goggles are pulled down over the eyes by the user that will now be exposed to white light stimuli of 200 milliseconds duration. Light stimuli are automatically emitted for the threshold measurements and will stop when the absolute threshold is measured, which in normal healthy adults typically occurs after 25-35 minutes from start.

Such a system implementation aims to be easy to use and operate avoiding the use of any skilled operator. In addition, the system requires minimal user training. Data are digitally stored

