Statistical Analysis Plan cover sheet

Wearable Dark-adaptometer in Normal Adult Healthy Volunteers

NCT number NCT02674425

Version 2.0 27/01/2017

WONDER STUDY
Evaluation of a novel wearable light-emitting system for measuring dark-adaptation thresholds in normal adult healthy volunteers

Statistical Analysis Plan

Chief Investigator: [name]
Principal Investigator: [name]
Co-Investigator: [name]
Collaborator: [name]

Clinical Eye Research Centre, St Paul's Eye Unit, Royal Liverpool University Hospital, [name]
University of Liverpool, Department of Eye and Vision Science, Institute of Ageing and Chronic Disease, [name]

Statistical Analysis Plan

Cone- and rod-mediated dark adaptation functions were expressed as log threshold luminance vs. time (minutes). The dynamics of participants' visual recovery after the bleach offset were determined by fitting established models of human dark adaptation to collected threshold data. Two models were used: 1) a bi-exponential model, fitting a single exponential function separately to the cone-mediated phase and the rod-mediated phase of dark adaptation; and 2) an exponential bi-linear model, fitting a single exponential to the cone threshold recovery data and 2 linear components (i.e., S2 and S3) to any rod threshold recovery data.

$$\begin{aligned}
 1) \quad D &= \underbrace{\theta_1 + \theta_2 \cdot \exp\left(\frac{-t}{\theta_3}\right)}_{\text{Cone}} + \underbrace{\eta_4 \cdot \exp\left(\frac{-(t - \theta_5) \cdot h(t, \theta_5)}{\eta_6}\right)}_{\text{Rod}} \\
 2) \quad D &= \underbrace{\theta_1 + \theta_2 \cdot \exp\left(\frac{-t}{\theta_3}\right)}_{\text{Cone}} + \underbrace{\theta_4 \cdot (t - \theta_5) \cdot h(t, \theta_5)}_{\text{S2}} + \underbrace{\theta_6 \cdot (t - \theta_7) \cdot h(t, \theta_7)}_{\text{S3}}
 \end{aligned}$$

$$h(t, \pi) = \begin{cases} 0 & \text{if } t - \pi \leq 0, \\ 1 & \text{if } t - \pi > 0. \end{cases} \quad h(t, \pi) = \frac{1}{(1 + e^{-k(t-\pi)})}$$

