Cone- and rod-mediated parameters were compared to previous literature on human dark adaptation to evaluate the performance of the developed dark adaptometer. Clinical data reported in [6] were particularly taken into consideration since a similar DA protocol was used by Jackson et al. to assess dark adaptation changes with age and as a function of decade. In addition, trial outcomes of interest were the test-retest and usability score results and variability obtained from participants after one or multiple DA visits.

Repeatability coefficient (RC) and within-case coefficient of variance (wCV) were calculated starting from the within-subject variance for each trial participant who completed at least 2 DA visits in order to assess variation in repeat measurements on the same patient. Intra-class correlation coefficient (ICC) – 2-way mixed-effects, absolute agreement, average measurement – was calculated for both

Group 1 and Group 2 through SPSS® Statistics V22.0 (IBM, Armonk, USA) to obtain the proportion of total variation in measurements by between-patient differences.

A pen-and-paper questionnaire as in Appendix 1-a was presented to participants twice on completion of the first and the third DA appointment. Seventeen questions targeting hardware and software implementation as well as personal feedback on the duration of the DA test were asked to rate comfort and ease of use of the developed system.

- [1] Alpern M. et al. Rhodopsin kinetics in the human eye. *Journal of Physiology*, 217 (1971), pp. 447-471.
- [2] W.A.H. Rushton, D.S. Powell. The rhodopsin content and the visual threshold of human rods. *Vision Research*, 12 (1972), pp. 1073–1081.
- [4] T.D. Lamb. Spontaneous quantal events induced in toad rods by pigment bleaching. *Nature*, 287 (5780) (1980), pp. 349-351.
- [5] T.D. Lamb. The involvement of rod photoreceptors in dark adaptation. *Vision Research*, 21 (12) (1981), pp. 1773-1782.

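### White-light thresholds and rod-cone break are compared with published values on one luminance scale, with no stimulus spectrum, no photopic or scotopic unit stated and no conversion planned

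*Protocol*

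**What the plan says.** **Stimulus.** Protocol section 4.3 has "the user that will now be exposed to white light stimuli of 200 milliseconds duration". The light comes from an OLED display behind an LCD filter, with its range given in cd/m². Section 4.8 again calls it white. No spectrum or colour temperature appears.

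**Scale.** The SAP states: "Cone- and rod-mediated dark adaptation functions were expressed as log threshold luminance vs. time (minutes". One axis serves both phases, and neither document says whether the luminance is photopic or scotopic.

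**Comparison.** The SAP says: "Cone- and rod-mediated parameters were compared to previous literature on human dark adaptation to evaluate the performance of the developed dark adaptometer". It gives particular weight to the 1999 ageing study, on the ground that its protocol was similar. Research question I (protocol section 3) asks whether the device at least matches commercial instruments and the literature. No second instrument is used in the study, so the answer rests on published values. Section 4.11 makes rod-cone break and absolute threshold the primary outcomes.

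**Colour.** Section 2 (Background) says: "The wavelength of the incident light has also a strong influence on the dark-adaptation curve". It later lists colour among the stimulus properties that matter ("Since the intensity, duration, colour, area and location of the light used for the fixation, bleach, and target stimuli all have an influence") and gives its response: "the modified 3-down-1-up staircase procedure carried out in [43] will be adopted here for comparison purposes with data results reported in the literature".

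**The concern.** Photopic luminance weights light by cone sensitivity. How strongly a given photopic cd/m² drives the rods depends on the spectrum, summarised by its scotopic/photopic ratio. Two white or coloured sources set to the same cd/m² can therefore differ in their effect on rods. Rod thresholds in cd/m² are comparable between instruments only if the spectra match or the values are converted.

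The rods' advantage over the cones also depends on the spectrum, so the time at which the rods take over can move as well. Both primary outcomes are exposed. Question I has no stated margin, so a modest artefact could make the device look better or worse than the literature with no real difference in performance.

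The plan recognises that colour matters, but its answer is to adopt a staircase. A staircase governs how luminance is stepped in response to the participant. It does not equate spectra or units.

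**Working it through.** The plan states no figure for this effect, so there is none to reproduce. The check asks how large the effect could be.

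**Inputs**
- From protocol section 4.8: in a healthy adult, rod-cone break at about 10⁻³ cd/m² and 7 min; absolute threshold at about 10⁻⁶ cd/m² and 30 min.
- Assumed: the scotopic/photopic ratios of the two sources differ by a factor r of 1.25, 1.5, 2 or 3. The documents give no ratio for the device or for any comparator.
- Assumed: a steeper rod slope of 0.3 log units/min as an alternative to the average derived below.
- Assumed: cd/m² is photopic, the spectrum does not change with stimulus level, and the cone threshold is flat near the break.

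**Step 1: threshold offset.** At rod threshold the same eye needs the same rod-effective (scotopic) luminance, which equals photopic luminance times the scotopic/photopic ratio. Photopic thresholds under two sources therefore differ by log₁₀(r).

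**Step 2: average rod slope.** (log₁₀10⁻³ − log₁₀10⁻⁶) / (30 − 7) = 3/23 = 0.130 log units/min.

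**Step 3: break-time shift.** Shift = offset / slope.

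| r (assumed) | Rod offset, log units | Shift at 0.130 log units/min | Shift at 0.3 log units/min |
|---|---|---|---|
| 1.25 | 0.097 | 0.7 min | 0.3 min |
| 1.5 | 0.176 | 1.4 min | 0.6 min |
| 2 | 0.301 | 2.3 min | 1.0 min |
| 3 | 0.477 | 3.7 min | 1.6 min |

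The 0.130 column probably overstates the shift. The interval from 7 to 30 min includes the final section, which section 2 of the protocol describes as approaching its limit asymptotically. The slope just after the break should be steeper than the end-to-end average. The threshold offset does not depend on the slope.

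**Step 4: what does not move.** A constant offset on a log scale cancels from any difference. It leaves the S2 and S3 slopes, the differences between visits, and the absolute repeatability of log thresholds as they were.

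**Step 5: if cd/m² is in fact scotopic.** Rod thresholds could then be set against scotopic published values, but cone thresholds would carry the offset instead. The break time in minutes would still depend on the spectrum, because no choice of unit changes when the rods overtake the cones.

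**The case against.** The strongest reply is that no mismatch has been shown. The only comparator singled out is the 1999 ageing study, and the documents do not give its target colour. It was chosen because its protocol was similar, and the Background links the choice of procedure to the very factors at issue, colour among them. This stands in part: the plan did take a step towards comparability, and the real offset could be nil. But similarity of colour is nowhere stated, and no step is planned to find out.

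A reader might infer that the device will be compared with tungsten or green-light instruments, because the Background describes a 1938 tungsten device and a later one "consisting of a single stimulus of a green (565 nm) solid-state light-emitting diodes (LEDs) as opposed to tungsten filaments". The documents do not support that. Both appear as instrument history, and neither is named as a comparator. The SAP's literature is open and excludes no source colour, but possible inclusion is not inclusion, so no offset specific to those instruments is used here.

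A reader might also infer that the white display will make the device look more sensitive. That would need the display spectrum and the comparator's, and neither is given.

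Two further points stand. The ratios are assumptions, and at the low end the effect is small: 0.1 log units equals the smaller luminance step of the psychomotor test in section 4.8. And the literature comparison has no formal test, so interpretation is at risk, not a formal decision.

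**Conclusion.** The gap is real and should be closed in the SAP. As written, the comparison of absolute threshold and rod-cone break with published values cannot separate device performance from source colour. Under assumed differences in scotopic/photopic ratio of 1.25 to 3 times, the rod threshold moves by about 0.1 to 0.5 log units. The break moves by about 0.7 to 3.7 min at the average slope, or 0.3 to 1.6 min at the assumed steeper one, against a benchmark of about 7 min. These ranges show what is possible. They do not estimate the bias in this study, whose size and direction the documents do not allow one to find. The point is confined to threshold level and break time against external data; the slope and within-study repeatability outcomes in Step 4 are outside it.

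**What to change.** Add a paragraph to the SAP that does the following.

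1. Obtain the spectrum of the display with its filter, from the manufacturer or a bench reading, and derive its scotopic/photopic ratio.
2. Report rod-phase thresholds, including absolute threshold, in scotopic cd/m² and cone-phase thresholds in photopic cd/m².
3. Convert each published value to the same unit where its spectrum or unit is reported, starting with the 1999 ageing study. Unit conversion does not correct a time in minutes, so where spectra differ, give the predicted shift beside the break-time comparison.
4. Where a source reports neither, keep it, but show the comparison of threshold level and break time with a stated range for the spectral offset. Do not use it to claim that the device matches or improves on that source.

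Keeping such sources matters: a rule that barred every source of unknown spectrum could remove the main named comparator.

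The cost is one spectrum, one conversion factor and a short SAP paragraph. Thresholds are stored as data files (protocol section 4.3), so they can be converted without retesting anyone. The downside is that some literature comparisons become less conclusive.

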4.4. Participants

Healthy adult volunteers with no prior or current eye problems and good general health will be recruited from University of Liverpool students and staff, Royal Liverpool University Hospital students, and people accompanying patients attending St. Paul's Eye Unit.

Two age-groups of subjects will be enrolled:

Group 1: 10 people aged 18 to 40

Group 2: 10 people aged 50 to 70

4.5. Inclusion criteria

Group 1 & 2

Healthy adult volunteers with no prior/current eye problems or family history of genetic eye diseases and good general health.

1. Refractive error: $\leq \pm 5$ dioptres spherical (myopia/hyperopia) equivalent; ≤ 3 dioptres cylinder (astigmatism) equivalent.

4.6. Exclusion criteria

Group 1 & 2

1. Subjects not in age range and/or unable to fully understand the informed consent and/or unable to comply with study procedures.
2. Self-reported history of depression, lack of sleep, psychiatric disorders, or neurological diseases such as Alzheimer's and Parkinson's disease.
3. Self-reported history of diabetes, epilepsy, stroke, or multiple sclerosis.
4. Self-reported hypovitaminosis A, alcoholism, liver or intestinal disease, malabsorption, protein calorie malnutrition, or sickle cell anaemia.
5. Use of psychoactive drugs (including lithium salts for mood stabilisation).
6. Use of dietary intake of ascorbic acid, vitamin A, B, E or other antioxidant supplements in the last two weeks.
7. Recurrent practice of activities that expose the retina to ultra-violet radiation such as sailing, fishing, sunbathing or tanning saloons.

4.7. Procedures

Subjects included in the study will undergo the following investigations:

1. Detailed personal medical history (age of participant, ethnicity, smoking, diet, etc.) and family history of eye diseases (15 minutes)
2. Retinal structure, visual and behavioural test series (45 minutes)

- Refractive error
- Distance Visual Acuity (DVA)
- SKILL card
- Contrast sensitivity
- Pupillometry
- Confrontational visual fields
- Direct ophthalmoscopy
- Psychomotor capability

3. System performance
 - Dark-adaptometry testing (45 minutes)
4. System usability (15 minutes)
 - Ad hoc pen-and-paper questionnaire to assess comfort and ease of use of the novel dark-adaptometer

Subjects will have investigations (1-2) during the screening phase.

Retinal structure, visual and behavioural tests (3) will be carried out once at baseline.

Follow-up visits include dark-adaptometry testing (4), which will be carried out 3 times over 3 weeks. A minimum 1-day window is required after each testing phase.

System usability (4) will be assessed twice, respectively upon completion of the first and the last dark-adaptometry testing visit.

[figure not shown]

Figure 2. Flow-chart of the study design and steps

4.8 Detailed description of investigations

Refractive error

The refractive error of the study eye will be obtained by means of objective and subjective refraction techniques.

An initial estimation of the refractive error will be obtained by retinoscopy, an objective technique that uses a handheld device called retinoscope. The retinoscope projects a beam of light into the eye which is reflected at the back of the eye, producing the so called “retinoscopic reflex”. The examiner will move the light of the retinoscope across the subject’s eye assessing the movement (speed and direction) of the retinoscopic reflex. This movement will be neutralised using spherical and cylindrical lenses, which will represent an estimate of the refractive error. Immediately after retinoscopy subjective tests (duochrome and Jackson crossed cylinders) will be performed to determine the refractive correction which gives the subject the most comfortable vision.

Retinoscopy requires the subject to look at the examiner’s light for a time period (approximately 5 minutes).

DVA

Distance visual acuity will be measured with glasses (i.e., best corrected) and without glasses (i.e., uncorrected) by using the Early Treatment Diabetic Retinopathy Study (ETDRS) 4 m charts. These charts contain 14 lines of 5 letters each, meaning that the space between the letters and the between lines decreases proportionally to the size of the letters. For the purpose of this study 2 ETDRS charts (right and left eye) will be used, placed over a standardised illuminated box (62.9 x 65.4 x 17.8 cm) to guarantee consistent illumination. VA will be measured monocularly (right eye always first) with the chart positioned 4 m away. The chart will be moved to 1 m if the subject cannot see the first 20 letters (4 lines). Letters correctly identified will be counted, adding 30 letters in those cases where the chart was not moved to 1 m. Results will be recorded as the number of letters read correctly as well as a logMAR score. If no letters are correctly identified at a distance of 1 m the examiner will record vision as “counting fingers”, “hand movement”, “light perception” or “no light perception”.

SKILL card

The Smith-Kettlewell Institute Low Luminance (SKILL) card will be used to measure spatial vision under conditions of reduced contrast and luminance. The SKILL card consists of two near acuity charts mounted back to back. One side of the card contains black letters on a dark grey background (designed to simulate reduced contrast and luminance conditions) whilst the other side has a high-contrast, black-on-white letter chart. Using the appropriate near correction each card will be successively presented at a distance of 40 cm. The SKILL score will be recorded as the difference in performance (number of letters) between the two cards.

Contrast sensitivity

Contrast sensitivity will be measured using a Near Pelli-Robson Contrast Sensitivity Card. The card uses the traditional optotypes found in the original Pelli-Robson chart (i.e., 6 letters per line arranged in groups of 3 with a decreasing contrast) but features an overall size of 22.86 x 29.53 cm. Using the appropriate near correction, subjects will read the letters from a distance of 40 cm, starting with the highest contrast, until they are unable to read two or three letters in a single group. A score is assigned based on the contrast of the last group in which two or three letters were correctly identified.

Pupillometry

Pupil size will be measured manually (with a ruler) in the same room where the visual assessment was performed, under a known level of illumination.

Confrontational visual fields

To examine the visual field of the right eye the examiner will ask the subject to cover their left eye using the palm of their hand and instruct them to look at a pen located in front of them (held by the examiner). The examiner will use a slowly wagging finger to check the extent of the subject's visual field superiorly, inferiorly, nasally, temporally and on the diagonals. The subject must indicate when the examiner's finger comes into view. The same procedure is used to test the visual field of the left eye, covering the right eye.

This test will only pick up large visual field defects.

Direct ophthalmoscopy

Direct ophthalmoscopy is a non-invasive technique used to examine the posterior pole of the eye (fundus). A beam of light is shone into the eye through the pupil using an instrument called ophthalmoscope (a device about the size of a flashlight). Using an ophthalmoscope the examiner can detect pathological changes in the retina such as abnormal blood vessels or haemorrhages.

Psychomotor capability

Participants will undergo a brief psychomotor test by using the novel dark-adaptometer in order to confirm their ability to comply with the study procedure and be trained for the follow-up phase visits. An intermittent white light of 200 milliseconds duration and luminance starting at $\sim 4.86 \text{ cd/m}^2$ is shone through the OLED display of the light-emitting goggles. Participants are asked to respond to the visible light stimuli with a button press on the handheld joystick of the novel dark-adaptometer. Luminance is decreased by 0.3 logarithmic units at each button press or increased by 0.1 logarithmic units at each missed button press. The test stops automatically when 3 dark-adaptation thresholds have been determined under the conditions described above. Participants must respond within a time interval of 750 milliseconds after each light onset in order to be considered capable to comply with the study.

Dark-adaptometry testing

Dark-adaptometry testing will be carried out by using the novel investigational system described in Section 4.3. Wearable goggles and joystick are given to participants in their switched-on status and held by the subject under test respectively on the forehead, with an elastic strap, and on the dominant hand. For hygienic safety purposes, a non-allergenic disposable tissue will be placed on top of the inner gasket of the goggles that will be in contact with participants' face. Where a disposable tissue would not be available, the inner gasket of the goggles will be accurately cleaned with a sterile isopropanol solution. Participants will sit comfortably throughout the test and wear disposable earphones playing music to drown out external noise and any auditory signals from the embedded electronics when light stimuli are emitted. Testing is non-invasive and is semi-automatic in that the subject under test is required to collaborate actively during the procedure in order to start it and go through it. A responsible collaboration throughout the test will be repeatedly encouraged as testing results are strictly based on the subject's response. The examiner will start the test by triggering a white flash of light through a standard camera flash (e.g., Canon Speedlite 540EZ – Guide Number 54, 1.2 ms duration). The flash will be channelled to the study eye and aims to photo-bleach, hence reset the photoreceptors of the retina. Immediately after the onset of the photo-bleaching flash, the goggles are pulled down over the eyes by the user that will now be exposed to intermittent white light stimuli. Light stimuli are shone automatically inside the goggles after the photo-bleaching flash and until the end of the test. Dark-adaptometry testing will last for about 25-35

minutes and will involve one eye only. This will be randomly allocated by the examiner or will be the only eye meeting the inclusion criteria. As the brightness of the intermittent light stimuli changes throughout the test as well as the time at which they are presented, participants are asked to press either of the joystick's buttons to indicate when the light is visible. The intermittent light features an initial brightness of approximately 4.86 cd/m^2 and becomes dimmer and dimmer overall. The test lasts until participants will not be able to identify any new light stimuli.

The absolute threshold will be the last measured threshold and recorded as the dimmest light that the subject can detect when the rod sensitivity of the study eye is maximum. In a healthy adult, the absolute threshold is typically equal to a logarithmic light intensity around 10^{-6} cd/m^2 at a time of around 30 minutes from the start of the test.

The examiner will monitor in real-time the testing results on a laptop, which is USB-connected to the frame of the goggles from the same side of the study eye. A best fit of collected threshold measurements will be calculated; from this fit, a biphasic curve is expected to be observed.

The rod-cone break will be identified as the point of phase-change in the calculated curve, which coincides with the point when rods become more sensitive than cones. In a healthy adult, the rod-cone break is typically equal to a logarithmic light intensity around 10^{-3} cd/m^2 at a time of around 7 minutes from the start of the test.

The slope of the rod-mediated response will be also calculated from the best fit of the collected threshold measurements. Particularly, the slope of the (second) S2 and (third) S3 rod-mediated component of recovery will be identified: these coincide with a long section of near linear slope following the initial rapid nonlinear increase in rod sensitivity.

An ad hoc pen-and-paper system usability questionnaire will be presented to participants twice upon completion of the first and the last dark-adaptometry testing visit. Participants will rate comfort and ease of use of the system on a scale of 1-10 through questions targeting hardware and software implementation as well as testing duration and expectations.

